3.5 Study Timeline

3.5.1 Primary Completion:

The study will reach primary completion 24 months from the time the study opens to accrual.

3.6 Study Completion:

The study will reach study completion 36 months from the time the study opens to accrual.

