13. Participants will undergo a safety follow-up at one time point within the time interval (day 2 – day 7) post-scan for blood sample collection for blood chemistry and hematology and also for observation for vital signs. For in-patients we will use the blood samples and vital signs

obtained as part of the standard of care by the Bone Marrow and Transplant group. Out-patients will have to return to the clinic for the safety follow up.

14. Adverse drug events will be recorded at one time point with the time interval of 2-7 days after [¹⁸F]F-AraG injection/scan in the case report form.
15. Patients in the high risk of developing GVHD arm will undergo the above protocol once more 10-17 days after the first scan.
16. A post safety follow up will be conducted for up to 6 months via chart review to assess progression or development of aGVHD.

Safety Follow-up [range: One time point within the interval (Day 2 to Day 7) post-scan

1. BP, HR, Temperature, Blood Oxygen %, and Respiratory Rate will be recorded.
2. Blood will be collected for CBC, and Metabolite Analysis.
3. Adverse events will be collected at one time point within the time interval (day 2 – day 7) post scan.

Healthy subjects and out-patients will need to come in to the clinic for the safety follow up. For in-patients (GVHD group)-we will obtain the blood samples and vital signs obtained as part of the standard of care by the Bone Marrow and Transplant group.

Subjects with suspected acute GVHD OR at high-risk of aGVHD will be followed for 6 months post their last scan to evaluate disease (progression/development) by chart-review.

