Table 6-3: Study Calendar for Patients at high risk of developing acute GHVD

a: Investigational Agent: Dose as assigned (5 mCi); route/schedule.

b: Albumin, alkaline phosphatase, total bilirubin, bicarbonate, BUN, calcium, chloride, creatinine, glucose, LDH, phosphorus, potassium, total protein, SGOT[21], SGPT[45], sodium.

c: Obtained as part of the standard of care by the Bone Marrow and Transplant group for in-patients (for in-patients)

d: Procedure may be done during screening period or on Day 1 prior to injection of study drug.

CONFIDENTIAL

- e: On Day 1: Scan 1: head to toe PET/CT scan 60 minutes post injection); OPTIONAL head to toe PET/CT scan 30-minutes post-injection;
On Day 11-18: Scan 2: head to toe PET/CT scan 60 minutes post injection); OPTIONAL head to toe PET/CT scan 30-minutes post-injection
- f: Chart review for up to 6 months post scan to monitor disease progression
- g: Collected at one time point within the time interval (day 2 – day 7) post-scan #1 and at one time point within the time interval (day 2 – day 7) post-scan #2

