9.1.2 Primary Outcome Measurement Time Points

Duration of the follow up will extend to 6 months post final scan for all aGVHD subjects by chart review.

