10.5.2 Analysis Plan

Although the study will have low power due to the constrained sample size, in addition to descriptive statistics we will perform the following statistical analyses:

- In the highly suspected group:
Spearman rank correlation between median or maximum SUV values across ROIs and disease severity
- In the high-risk group:
Spearman rank correlation between SUV values in the first and second scans prediction of disease status at end of follow-up (aGVHD or no aGVHD) from SUV values of the first and second scans (using logistic regression)

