10.8 Accrual estimates

We expect the accrual of 5 healthy volunteers and 25 patients over 24-36 months.

Approximately 1-2 high risk patients for GVHD are seen monthly in the Bone Marrow and

Transplant clinic at Stanford Cancer Institute. Established GVHD patients are frequently seen in the clinic (approximately 5 high intensity and 10 low intensity patients at a given time). We consider this planned accrual achievable given our experience with other protocols and the expressed support from the referring physicians, [name] and [name].

We plan to prioritize patients from Arm 1; imaging up to 10 patients highly suspected to have aGVHD and analyze scans to ascertain if the tracer is able to image the disease, before recruiting patients from Arm 2 (those that are at high risk of developing the disease post transplant).

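### The follow-up window behind the Arm 2 primary outcome is stated inconsistently, overruns the study calendar if accrual is slow, and has no rule for incomplete observation

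*Combined protocol and SAP*

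**What the plan says.** **Length and starting point of follow-up**
- Section 5.1, GVHD patient protocol, step 16: "A post safety follow up will be conducted for up to 6 months via chart review to assess progression or development of aGVHD". This is a maximum, with no starting point.
- Section 5.1, last paragraph of the safety follow-up, on both GVHD groups: "will be followed for 6 months post their last scan to evaluate disease (progression/development) by chart-review". This is fixed, from the last scan.
- Section 9.1.2: "Duration of the follow up will extend to 6 months post final scan for all aGVHD subjects by chart review". This is also fixed.
- Table 6-2, footnote f: "Chart review for up to 6 months post scan to monitor disease progression". Footnote f of Table 6-3 has the same wording, and the column headings of both tables also give a maximum. Arm 2 patients have two scans, and Table 6-3 does not say which one starts the clock.

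**Use of the window.** Section 9.1.1 makes development of aGVHD, monitored after the second scan, the primary outcome variable of the high-risk group. Section 10.5.2 plans a logistic regression for "prediction of disease status at end of follow-up (aGVHD or no aGVHD", with SUV from both scans as predictors.

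**Calendar**
- Section 3.5.1 puts primary completion at 24 months from opening to accrual.
- Section 3.6: "The study will reach study completion 36 months from the time the study opens to accrual".
- Section 10.8: "We expect the accrual of 5 healthy volunteers and 25 patients over 24-36 months". It also plans to image and analyse up to 10 Arm 1 patients before recruiting Arm 2.

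**The concern.** A yes/no outcome needs one observation window that is the same for everyone. Here the window may or may not be a full 6 months, depending on the section read, and it starts from the last scan, an unspecified scan or nothing stated. The accrual and completion dates allow a situation in which the latest Arm 2 patients cannot have 6 months of chart review before the study completes.

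The outcome in 10.5.2 has two values and comes from chart review. A chart with no aGVHD entry may mean that the patient stayed free of it for 6 months, or that nobody looked for long enough. The plan does not separate the two. If future cases were counted as free of aGVHD and the tracer works, their high SUV would appear as false alarms. The pilot would then understate the predictive power that section 1.1 calls the ultimate goal, and that would feed the phase II decision in 10.9. With about 12 patients in the arm, one or two such cases matter.

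**Working it through.** The plan gives no derivation of its 24- or 36-month dates, so there is no calculation to reproduce. The check is calendar arithmetic, at 30.4375 days per month.

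**Inputs.** Accrual lasts A = 24 to 36 months (10.8). The second scan is at day 14-21 after transplant (2.6), or 0.46-0.69 months. Follow-up is 6 months (9.1.2). Primary completion is month 24 and study completion month 36 (3.5.1, 3.6). Up to 25 GVHD patients are planned, roughly half per group (10.7), so about 12.5 in Arm 2.

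**1. End of full follow-up for the last patient** = A + second-scan lag + 6.
- A = 24: 24 + 0.46 to 0.69 + 6 = month 30.5 to 30.7. This fits month 36.
- A = 36: 36 + 0.46 to 0.69 + 6 = month 42.5 to 42.7. This misses month 36 by 6.5 to 6.7 months.

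**2. Latest Arm 2 transplant that allows full follow-up**
- By month 36: 36 - 6 - (0.46 to 0.69) = month 29.3 to 29.5.
- By month 24: 24 - 6 - (0.46 to 0.69) = month 17.3 to 17.5. Accrual is expected to take at least 24 months, so the Arm 2 primary outcome cannot be complete at month 24 for patients recruited up to then.

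**3. Share of Arm 2 cut short at month 36.** Assumptions: even accrual, Arm 2 opening after 10 of 25 patients (month 0.4A) and running to month A, and accrual dated at the first scan. The second scan follows 10-17 days later (5.1, step 15), midpoint 13.5 days or 0.44 months. The threshold is then 36 - 6 - 0.44 = month 29.56, and share = (A - 29.56) / (0.6A), or 0 if negative.

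| Accrual A (months) | Calculation | Share | Of 12.5 patients |
|---|---|---|---|
| 29 or less | negative | 0% | 0 |
| 30 | 0.44 / 18.0 | about 2.5% | 0.3 |
| 33 | 3.44 / 19.8 | 17% | 2.2 |
| 36 | 6.44 / 21.6 | 30% | 3.7 |

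Dating from transplant instead (threshold 29.31-29.54) gives 17-19% at 33 months and 30-31% at 36. If Arm 2 recruited from month 0, 3 of 12-13 evenly spaced patients would be cut short at A = 36.

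**4. Illustration: cases missed if cut-short patients were counted as free of aGVHD.** Take A = 36, 12 evenly spaced patients and a second scan at day 21. The last four have 4.7, 2.9, 1.1 and 0 months of follow-up. Section 2.1 gives incidences of 20-50% (related donors) and upwards of 70% (matched unrelated donors). The documents give no onset timing, so both patterns below are assumptions.
- Uniform onset over 6 months: the missed fractions sum to 0.215 + 0.515 + 0.815 + 1 = 2.545. Times 0.2, 0.5 and 0.7, that is 0.5, 1.3 and 1.8 missed cases.
- 80% of onsets in the first 2 months, the rest uniform: the sum is 0.0645 + 0.1545 + 0.556 + 1 = 1.775, giving 0.35, 0.9 and 1.2.

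Expected true cases are 2.4, 6.0 and 8.4 of 12.

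**The case against.** **The calendar may never bind.** The overrun at month 36 is conditional. Section 10.8 reports 1-2 high-risk patients a month. If all enrolled, 12.5 patients would take 6.25 to 12.5 months. Even with Arm 2 opening at month 14.4 (0.4 of 36), accrual would end at about month 21 to 27 with nobody cut short. This stands: 30% is the worst corner of a range that includes 0. Lower uptake would lengthen accrual, however, and 36 months is the plan's own upper figure.

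**The plan does not score short follow-up as no aGVHD.** A reader might infer that it does, because there are only two outcome values and no third category. The documents do not support that. No section gives a scoring rule, and the same silence would allow an unobserved outcome to be treated as missing. Nor does any section say that chart review stops at month 36. What stands is that the rule is absent.

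**Death, relapse and graft failure are not lost observations.** A reader might add them to the unobserved cases. The documents do not support that either. Nothing ends chart review at relapse or graft failure, and a patient who dies without aGVHD truly did not develop it. Death is a competing event to be reported, not a reason for exclusion.

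**Partly handled, and only a pilot.** Section 9.1.2 governs outcome timing and fixes 6 months, and sections 10.5.2 and 10.7 disclaim power. Both points are fair. But step 16 and the calendars, which staff will follow, say otherwise, and low power does not excuse an outcome that can be measured over unequal periods.

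**Conclusion.** The concern holds in a limited form. The wording conflict is certain: two fixed statements stand against step 16, two footnotes and two column headings, and the starting points differ. The dates conflict at the upper end of accrual. Full follow-up could run to month 42.5-42.7 against study completion at month 36, with truncation only if Arm 2 accrual passes about month 29.3-29.5. Primary completion at month 24 conflicts more firmly, if it means that primary-outcome data are complete; section 3.5.1 does not define it.

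The size ranges from no Arm 2 patient cut short at 29 months of accrual or less to about 17% at 33 months and 30% at 36. This rests on even accrual and on Arm 2 opening after 10 of 25 patients. Counting such patients as aGVHD-free would miss about 0.4 to 1.8 cases in the slowest scenario, under assumed onset patterns. That scoring is possible under the plan but not stated in it. Withdrawal (5.2) can also end observation early at any accrual speed, and it has no rule either. The change should be made because it is cheap and protects a primary outcome.

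**What to change.** 1. Remove the maximum wording from step 16 of the GVHD patient protocol and from the headings and footnote f of Tables 6-2 and 6-3, so that all match 9.1.2. State one window and one starting point for every Arm 2 patient.
2. Restate 3.5.1 and 3.6 so that primary and study completion follow the last patient's 6-month chart review.
3. In 10.5.2, treat patients whose observation ends early without aGVHD, through withdrawal, transfer of care or cut-off, as outcome not observed rather than as free of aGVHD.
4. Add a sensitivity analysis of time to onset, censored at the last date known free of aGVHD. Section 7.2 already records the onset date. This matters because the yes/no model would keep early known cases while leaving out early-ended patients without aGVHD, which tends to overstate risk.
5. Continue chart review after relapse or graft failure, and report death without aGVHD as a competing event rather than excluding it.

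**Cost.** Wording changes and some extra chart review, with no new scans or visits. If accrual runs to month 36, closure for chart review moves by about 6-7 months (42.5 to 42.7 against 36). A few patients may fall outside the yes/no model.

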5.2 Criteria for Removal from Study

Withdrawal of Participants

The Protocol Director may withdraw participants from the study for one or more of the following reasons: failure to follow the instructions of the Protocol Director and/or the study staff; failure to provide informed consent; determination that continuing the participation could be harmful to the subject; the study is cancelled or other administrative reasons.

Discontinuation: Patients can discontinue in case of unacceptable adverse events or patient decision to withdraw from study.

6 STUDY CALENDAR

6.1 Healthy Volunteers

Table 6-1: Study Calendar for Healthy Volunteers

	Screening	Day 1			Safety Follow-Up
	Day -30 to Day 1 pre-injection	Pre-injection of [¹⁸ F]F-AraG (Baseline)	Injection of [¹⁸ F]F-AraG ^a	Post-injection of [¹⁸ F]F-AraG	Day 2-7 post-scan
Inclusion/Exclusion Criteria	X				
Informed Consent	X ^d	X ^d			
hCG ^c	X ^d	X ^d			
Height		X			
Weight		X			
Vital signs		X		X	X
EKG		X (leads placed prior to scan)	X	X	
CBC w/diff, plts		X			X
Serum chemistry ^b		X			X
IV administration of [¹⁸ F]F-AraG			X		
PET/CT scan with investigational Agent [¹⁸F]F-AraG				X ^e	
Arterial/venous blood sampling for input function				X (0, 1, 3, 5 10, 15, 30, 45, 60 and 90 min after tracer injection)	
Radio-Metabolite Analysis				X (0, 1, 3, 5 10, 15, 30, 45, 60 and 90 min after tracer injection)	
Adverse event evaluation				X	X ^f

a: Investigational Agent: Dose as assigned (5 mCi); route/schedule.

b: Albumin, alkaline phosphatase, total bilirubin, bicarbonate, BUN, calcium, chloride, creatinine, glucose, LDH, phosphorus, potassium, total protein, SGOT[21], SGPT[45], sodium.

c: Urine or serum pregnancy test (women of childbearing potential).

d: Procedure may be done during screening period or on Day 1 prior to injection of study drug.

e: Scan 1: 30-minute dynamic PET of heart (60x5s+25x1min); Scan 2: vertex to mid-thigh static PET 60-minute post injection (includes brain); Scan 3: vertex to thigh static PET 90 minutes post-injection

f: Collected at one time point within the time interval (day 2 – day 7) post scan.

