These preliminary studies in healthy human volunteers have been promising with low background in the thorax and GI tract, making it favorable for thoracic and pelvic imaging. Favorable kinetics of [¹⁸F]F-AraG in humans along with the preclinical data support its potential as a promising tracer for early detection of GVHD and warrants its further clinical evaluation in aGVHD patients. Given the paucity of PET tracers for activated T cells in the clinic this work lays the important foundation for [¹⁸F]F-AraG PET imaging in aGVHD patients and the potential to provide crucial information to aid in the detection of activated T cell dynamics during the activation phase of aGVHD.

Organs	Male	Female
Adrenals	0.046567	0.067133
Brain	0.006380	0.007407
Breasts	0.005757	0.007547
Gallbladder Wall	0.051400	0.063033
LLI Wall	0.085107	0.012150
Small Intestine	0.047033	0.073000
Stomach Wall	0.018667	0.025367
ULI Wall	0.022600	0.033067
Heart Wall	0.052533	0.096933
Kidneys	0.877000	1.133333
Liver	0.211000	0.266667
Lungs	0.027167	0.033133
Muscle	0.009190	0.012167
Ovaries		0.016967
Pancreas	0.037300	0.050200
Red Marrow	0.013600	0.016833
Osteogenic Cells	0.007390	0.010593
Skin	0.004543	0.005790
Spleen	0.093600	0.163667
Testes	0.002780	
Thymus	0.005710	0.007800
Thyroid	0.001357	0.001633
Urinary Bladder Wall	0.085800	0.088167
Uterus	0.014133	0.017500
Total Body	0.018767	0.025200
Effective Dose	0.0138 mSv/MBq	

Table 2: [¹⁸F]F-AraG human radiation dosimetry data. Mean radiation dosimetry data in 3 males and 3 females in REM/mCi. The kidneys receive the highest radiation dose followed by the liver.

For our studies at Stanford, the tracer will be administered as a single bolus injection of approximately 5 mCi into a hand or arm vein. The rationale for the starting dose is based on dosimetry studies already performed in healthy human volunteers where the dose limiting organ was found to be the kidney and the annual dose characterized as 5mCi. Please refer to the imaging protocol for recommended limits for male and female subjects. The major route of clearance based on initial clinical studies is the liver and kidney.

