4 IMAGING AGENT/DEVICE/PROCEDURE INFORMATION

4.1 $[18\text{F}]\text{F-AraG}$: 2'-deoxy-2'-[18F]fluoro-9- β -D-arabinofuranosyl guanine

The imaging agent to be used in this study is 2'-deoxy-2'-[18F]fluoro-9- β -D-arabinofuranosyl guanine. The radionuclide on this imaging agent being Fluorine-18 (^{18}F). The imaging agent will be administered intravenously.

Clinical grade imaging agent will be synthesized under GMP/GLP conditions at the Lucas Center Cyclotron and Radiochemistry facility, part of the Molecular Imaging Program at Stanford. The imaging agent will be requested as and when subjects become available. The radiotracer will be received at the Nuclear Medicine department at Stanford Hospital in a lead shielded container by an authorized person and with the appropriate transfer sheet.

Dosimetry of this imaging agent has previously been characterized in male and female healthy subjects and the information is included on page 21. Dosimetric calculations were performed

using the OLINDA/EXM 1.1 software using methods previously described using other tracers [Yaghoubi, 2001].

PET/CT is a well established, FDA approved clinical imaging procedure. Each subject will be scanned a maximum of 2 times. For each imaging session the amount of radioactivity that will be administered will be less than 5.7 and 4.4 mCi for males and females respectively.

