5 STUDY PROCEDURES

5.1 Imaging Protocol for Patient Groups

Each subject may have up to two imaging sessions. The procedures for each imaging session is detailed below:

Day 1 (Imaging Day)

Overview of procedures prior and post injection of [¹⁸F] F-AraG:

1. Subject will participate in an informed consent session (approximately 30 minutes) and if she/he would like to continue after being fully informed she/he will sign consent form.
2. Subject will be asked to drink several glasses of water before arriving at the nuclear medicine clinic and during the study.
3. Subject will be interviewed to obtain medical history.
4. Volunteer height and weight will be measured.
5. Baseline Heart Rate (HR), Blood Pressure (BP), Blood Oxygen %, Temperature, and Respiratory Rate will be collected at baseline (5-120 minutes prior to the injection of the tracer).
6. IV line may be placed in both arms of healthy subjects for PET tracer injection and another may be used for blood collection. The GVHD patients will have double lumen catheters which can these be used for these purposes.
7. For baseline CBC analysis- 3 ml of blood will be collected and 5 ml of blood will be collected for baseline metabolic panel analysis.
8. Subject may either be positioned on the PET/CT scanner bed or another bed in the clinic (where possible the same PET-CT system should be used especially for the healthy subjects).
9. Injection of [¹⁸F] F-AraG and post-injection procedures will follow.
10. If possible, subjects should be asked to urinate prior to the start of the PET/CT scans.
11. A bolus < 5.7 mCi of clinical grade [¹⁸F] F-AraG for male volunteers or < 4.4 mCi of clinical grade [¹⁸F]F-AraG for female volunteers will be injected through IV.
12. A CT image will be acquired with the PET images.
13. The PET scanning procedure may start at the time of tracer injection or at a later time point after tracer injection. The imaging field includes the vertex to thigh for healthy subjects and vertex to feet for GVHD patients. Up to two whole-body PET scans may be performed at various time points after injection of the tracer, not to exceed 2 hours after tracer injection.
14. Blood pressure, Temperature, Blood Oxygen saturation, Heart Rate, Respiratory Rate will be measured immediately after [¹⁸F]F-AraG PET-CT procedure.
15. A safety follow up will happen at one time point within the time interval (day 2 – day 7) post-scan.
16. All observed adverse events and subject complaints will be recorded.

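### Footnote a of all three study calendars gives 5 mCi for every subject, 13.6% above the protocol's own per-session limit for women

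*Combined protocol and SAP*

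**What the plan says.** **Calendars.** Footnote a of Tables 6-1 (healthy volunteers), 6-2 (highly suspected aGVHD) and 6-3 (high risk of aGVHD) is the same each time: "Investigational Agent: Dose as assigned (5 mCi); route/schedule". It is attached to the injection column. It does not mention sex and does not refer to another section.

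**Limits.** Section 4.1 sets a cap per session: "For each imaging session the amount of radioactivity that will be administered" "will be less than 5.7 and 4.4 mCi for males and females respectively". Section 5.1 step 11 repeats the caps ("for male volunteers or < 4.4 mCi of clinical grade" tracer for women). Step 11 speaks of volunteers, but step 13 of the same list names both kinds of participant: "The imaging field includes the vertex to thigh for healthy subjects and vertex to feet for GVHD patients". The list therefore covers all cohorts, and 4.1 is not restricted by cohort in any case.

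**Background.** Section 2.2 describes a "single bolus injection of approximately 5 mCi" and shortly afterwards adds "Please refer to the imaging protocol for recommended limits for male and female subjects".

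**Radiation dose.** Table 2 in section 2.2 prints one effective-dose coefficient, "0.0138 mSv/MBq". Section 7.1 gives tracer doses of 2.7 mSv from 163 MBq for women and 3.3 mSv from 211 MBq for men, then adds the CT dose. It does not name the coefficients behind those figures.

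**The concern.** The calendar is the page that staff are likely to have in front of them at a visit, and its only number for activity is 5 mCi. For a woman that figure is higher than sections 4.1 and 5.1 permit. If a dose were ordered or checked against the calendar, it would break the protocol's own limit.

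The limit by sex looks deliberate. Section 2.2 names the kidney as the dose-limiting organ, and Table 2's kidney values bring the two caps to almost the same kidney dose (see the working). A single figure for both sexes loses that distinction.

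The exposure figures raise a smaller question. Section 7.1 describes radiation given for research only, and a reader who tries to reproduce its tracer doses from the one effective-dose coefficient in the protocol cannot do so.

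**Working it through.** **1. Calendar activity against the limits**

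Inputs: 5 mCi (footnote a, all three tables); <4.4 mCi for women and <5.7 mCi for men (4.1 and 5.1 step 11); 1 mCi = 37 MBq.

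- In MBq: 5 × 37 = 185; 4.4 × 37 = 162.8; 5.7 × 37 = 210.9.
- Women: 5/4.4 − 1 = +13.6%, above the limit.
- Men: 5/5.7 − 1 = −12.3%, within the limit.

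The activities in 7.1, 163 and 211 MBq, are the caps of 4.4 and 5.7 mCi after rounding. Sections 4.1, 5.1 and 7.1 therefore agree with one another, and the footnotes are out of line.

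**2. Is the split by sex deliberate?**

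Inputs: Table 2 kidney values, 1.1333 rem/mCi (women) and 0.877 rem/mCi (men).

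| | At the cap | At 5 mCi |
|---|---|---|
| Women | 1.1333 × 4.4 = 4.99 rem | 1.1333 × 5 = 5.67 rem |
| Men | 0.877 × 5.7 = 5.00 rem | 0.877 × 5 = 4.39 rem |

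Both caps correspond to a kidney dose of about 5 rem. The protocol does not say that the caps were derived this way, so this is an inference.

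**3. Query: the 7.1 tracer doses against Table 2**

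First, the sums in 7.1 reproduce. For healthy subjects, 2.7 + 9 = 11.7 and 3.3 + 9 = 12.3 mSv. For GVHD patients with one CT, 2.7 + 3 = 5.7 and 3.3 + 3 = 6.3 mSv. Only the tracer term is in question.

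Tracer dose = activity × coefficient:

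- Women: 163 × 0.0138 = 2.25 mSv, against 2.7 stated. Gap 0.45 mSv (20%).
- Men: 211 × 0.0138 = 2.91 mSv, against 3.3 stated. Gap 0.39 mSv (13%).

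Rounding does not close the gap. With every figure rounded in the direction that shrinks it:

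- Women: 2.65 − 163.5 × 0.01385 = 2.65 − 2.264 = 0.39 mSv.
- Men: 3.25 − 211.5 × 0.01385 = 3.25 − 2.929 = 0.32 mSv.

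Coefficients consistent with 7.1:

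- Women: 2.65/163.5 = 0.0162 to 2.75/162.5 = 0.0169 mSv/MBq.
- Men: 3.25/211.5 = 0.0154 to 3.35/210.5 = 0.0159 mSv/MBq.

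The two ranges do not overlap, and both lie above 0.0138. So 0.0138 cannot be an average of two unprinted coefficients by sex. Using 5 mCi instead does not help: 185 × 0.0138 = 2.55 mSv, which matches neither figure.

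Relative to the stated session totals, the gap is 0.45/5.7 = 7.9% (women) and 0.39/6.3 = 6.2% (men) for GVHD patients with one CT. For healthy subjects it is 0.45/11.7 = 3.9% (women) and 0.39/12.3 = 3.2% (men).

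**The case against.** **On the footnote.** It looks like template shorthand: the route and schedule are left unfilled, and the reference to an assigned dose can be read as deferring to wherever the dose is set. Every section that sets a limit sets it by sex, and 2.2 sends the reader to those limits. On this view the calendars lack only a cross-reference.

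Much of this stands. Step 11 sets the limit, and 2.2 needs no rewording. But the footnotes contain no pointer of their own, and the one number they print is not allowed for women.

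A reader might go further and infer that women in this trial are, or will be, given too much tracer. The documents do not support that. Step 11 is the injection instruction, and 7.1 has each dose double checked by a researcher and a technologist. A reader might also infer that two sessions in the high-risk group breach a cumulative limit. Section 4.1 states its caps per session and allows two sessions. Section 2.2 mentions an annual figure of 5 mCi in passing but does not set it out as a ceiling.

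**On the exposure figures.** Section 7.1 does not claim to rest on Table 2. Section 2.3 says that the company holding the IND has done its own dosimetry, which cannot be seen here. Separate coefficients by sex, higher in women, would fit the pattern of Table 2's organ doses. This objection stands in full: a reader might infer that 7.1, or Table 2, is wrong, but the documents do not show which, or that either is. If 0.0138 is the right basis, 7.1 overstates exposure, which is the cautious direction.

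**Conclusion.** The point holds as a minor inconsistency in an operational part of the protocol. In all three calendars the printed activity is 13.6% above the per-session limit for women, and it is within the limit for men. This rests only on the protocol's own figures and a unit conversion. It is not evidence of overdosing.

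The mismatch between 7.1 and Table 2 (0.45 mSv in women, 0.39 mSv in men) is real as arithmetic. Treating it as an error would assume that 7.1 was meant to follow from Table 2, which the documents do not say. It remains a sourcing query.

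No endpoint, sample size or analysis depends on either matter.

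**What to change.** **Footnotes.** In Tables 6-1, 6-2 and 6-3, replace footnote a with: *Investigational Agent: single IV injection per 5.1 step 11: <5.7 mCi (men), <4.4 mCi (women)*. Remove the 5 mCi figure. Keeping it as a nominal value beside the limits would leave the conflict for women in place. Leave 2.2 as it is.

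**Query to the sponsor.** Check the source dosimetry behind the tracer doses in 7.1 and state the coefficients used, with their source. Change neither 7.1 nor Table 2 before that check. In particular, do not replace Table 2's coefficient with values worked back from 7.1.

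**Cost.** Three footnotes and, once the check is done, probably one sentence in 7.1. Under 8.1 a protocol change goes to the FDA as a modification and needs IRB and SRC approval, so it is sensible to include it in the next amendment. Design, procedures and analysis do not change.
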